#### **8.4.2 Study Drug Exposure**

Study drug exposure and compliance in the phase 1b will be listed for the Safety population.

Compliance will be calculated as: [(total number of dose of drug administered during treatment period)/ (total number of dose planned to administer during treatment period)] \*100%

#### **8.4.3 Adverse Events**

Listings will be provided for all reported treatment-emergent adverse events (TEAEs), defined as AEs that started or worsened in severity on or after the date of the first dose of study drug through 30 after the end of treatment, or prior to initiation of another investigational agent or cytotoxic chemotherapy. Missing or partially missing start and end dates for AEs and SAEs will not be imputed. For cases in which it is not possible to ascertain treatment-emergence, the event will be classified as treatment-emergent.

The reported AE term will be coded using the Medical Dictionary for Regulatory Activities (MedDRA) version 24.0. The severity of each AE will be graded by the Investigator based on version 5.0 of the National Cancer Institute (NCI) Common Terminology Criteria for Adverse Events (CTCAE). If a severity grading scale does not exist for an AE, the Investigator will classify the severity as mild, moderate, severe, life-threatening/debilitating, or fatal based on the criteria described in the study protocol. The causal relationship between the occurrence of an AE and study drug will be judged by the Investigator as “probable”, “possible”, “unlikely”, or “unrelated”.

The following listings will be presented for part 1a:

- All TEAEs
- Treatment-emergent serious adverse events (SAEs)
- TEAEs leading to discontinuation of study drug

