#### 7.5.5. Post-Treatment Monitoring for Hematologic Second Primary Malignancy

Post treatment monitoring as clinically indicated will be performed for those subjects who 1) do not enroll in a new clinical study, 2) do not withdraw consent and 3) do not begin a new anti-neoplastic therapy. Monitoring will include a complete blood count with at least an automated differential or peripheral blood smear.

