### **13.2.2. Serious Adverse Event (SAE)**

An SAE is any untoward medical occurrence that at any dose meets any of the following:

- Results in death (regardless of cause, that occurs during participation in the study or occurs after participation in the study and is suspected of being a delayed toxicity due to administration of study drug)
- Is life-threatening (an event/reaction in which the subject was at risk of death at the time of the event/reaction; it does not refer to an event/reaction which hypothetically might have caused death if it were more severe).

*Note:* Life-threatening AE or life-threatening suspected adverse reaction: An AE or suspected adverse reaction is considered "life-threatening" if, in the view of either the Investigator or Sponsor, its occurrence places the subject at immediate risk of death. It does not include an AE or suspected adverse reaction that, had it occurred in a more severe form, might have caused death.

- Requires in-subject hospitalization or prolongation of hospitalization
- Results in persistent or significant disability or incapacity, or

*Note:* the term disability means a substantial disruption of a person's ability to conduct normal life functions. This definition is not intended to include experiences of relatively minor medical significance such as uncomplicated headache, nausea, vomiting, diarrhea, influenza, and accidental trauma (eg, sprained ankle), which may interfere or prevent everyday life functions but do not constitute a substantial disruption.

- Results in a congenital abnormality or birth defect
- It is an important medical event that may jeopardize the subject or may require medical intervention to prevent 1 of the outcomes listed in the definition.
- All SAEs that occur after any subject has been enrolled, before treatment, during treatment, or within 30 days following the cessation of treatment, whether or not they are related to the study, must be recorded on forms provided by Epizyme, Inc.

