## **13.3. Recording Adverse Events**

Adverse events spontaneously reported by the subject and/or in response to an open question from the study personnel or revealed by observation will be collected from the time the subject

signs the informed consent form until the end of the safety reporting period (or until screen failure). The safety reporting period ends at the time of the safety follow-up visit, 30 days after the last dose of study drug, or initiation of an investigational agent or anticancer therapy, whichever occurs first.

The AE term should be reported in standard medical terminology when possible. For each AE, the Investigator will evaluate and report the onset (date and time), resolution (date and time), intensity, causality, action taken, serious outcome (if applicable), and whether or not it caused the subject to discontinue the study.

Subjects who experience death while on treatment or within 30 days of study drug discontinuation ('deaths on study' hereafter) will have a Grade 5 SAE reported in electronic data capture (EDC) system and an SAE form submitted UNLESS the only known cause of death is progressive disease. Attempts should be made to specify a cause of death. However, if progressive disease or the indication of the study is the only known cause of death, the death is not untoward and should be recorded on the Death eCRF as progression of disease is a key efficacy criterion.

All deaths on study, regardless of cause, or if meeting the criteria for a reportable SAE will be reported on the Death eCRF.

Should a pregnancy occur, it must be reported and recorded on Epizyme, Inc.'s pregnancy form. Pregnancy in itself is not regarded as an AE unless there is a suspicion that an IP may have interfered with the effectiveness of a contraceptive medication.

The outcome of all pregnancies (spontaneous miscarriage, elective termination, normal birth, or congenital abnormality) must be followed up and documented even if the subject was discontinued from the study.

All reports of congenital abnormalities/birth defects are SAEs. Spontaneous miscarriages should also be reported and handled as SAEs. Elective abortions without complications should be reported as AEs but recorded as planned procedures within the eCRF.

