#### **14.6.2. Adverse Events**

Treatment-emergent adverse events (TEAE) is defined as AEs that started or worsened in severity on or after the date of the first dose of the study drug through 30 days after the end of treatment.

The reported AE term will be coded using the Medical Dictionary for Regulatory Activities (MedDRA) version in effect at the time of the database lock. The severity of each AE and abnormal laboratory tests will be graded by the site investigator based on version 5.0 of the NCI CTCAE. If a severity grading scale does not exist for an AE, the investigator will classify the severity as mild, moderate, severe, life-threatening/debilitating, or fatal based on the criteria described in the study protocol. The causal relationship between the occurrence of an AE and study drug will be judged by the investigator as “probable”, “possible”, “unlikely”, or “unrelated”.

Incidence of TEAEs will be summarized for all analysis groups (see Section 14.4) in dose escalation part and cohort groups in dose expansion part, and by MedDRA system organ class (SOC) and preferred term (PT) within each SOC. Overall incidence will also be presented for each part. TEAEs will also be summarized by severity, and by relationship to study intervention. If a subject experience repeat episodes of the same AE (as defined by the MedDRA SOC and PT), then the event with the highest reported severity grade and the strongest causal relationship (“related”) to study drug will be used for purposes of the incidence tabulations.

All AEs including TEAEs will be presented in study phase specific listings (Phase 1 dose escalation part and Phase 1b dose expansion part).

The number (percentage) of subjects with TEAEs leading to discontinuation from study drug will be summarized by MedDRA SOC and PT for each group (the analysis groups in dose escalation part or cohort groups in dose expansion part). Subject data listings of all AEs leading to discontinuation from study drug will also be provided for the phases.

Serious adverse events will be summarized as for TEAE, ie, by the analysis group, SOC and PT, and by severity and relationship to the study drug. All SAEs will also be presented in listings.

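### SAP 8.4.3 lists only treatment-emergent events, so a reported serious adverse event with known onset outside that window would be in none of its adverse event listings

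*SAP*

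**What the plan says.** **SAP 8.4.3** sets the scope: "Listings will be provided for all reported treatment-emergent adverse events (TEAEs), defined as AEs that started or worsened in severity". It names three listings: all treatment-emergent adverse events (TEAEs), treatment-emergent serious adverse events (SAEs), and TEAEs that led to stopping study drug. The window opens at first dose and runs "through 30 after the end of treatment, or prior to initiation of another investigational agent or cytotoxic chemotherapy". No unit follows the 30, and nothing says which limb prevails. There is one default: "For cases in which it is not possible to ascertain treatment-emergence, the event will be classified as treatment-emergent".

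**Protocol 14.6.2** planned more: "All AEs including TEAEs will be presented in study phase specific listings", and "All SAEs will also be presented in listings". It also planned a listing of all adverse events leading to discontinuation.

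**Which document controls.** Protocol 14.2 lets the SAP prevail where the two differ on planned analyses. SAP section 1 says the clinical study report is prepared from the SAP. SAP 2.2 says only that, after early termination, a selection of the phase 1a analyses will be done.

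**Post-treatment monitoring and reporting.** Protocol 7.5.5 states: "Post treatment monitoring as clinically indicated will be performed for those subjects who 1) do not enroll in a new clinical study". It further limits this to subjects who have not withdrawn consent or begun new anti-neoplastic therapy, and it gives no end date. Section 13.2.2 requires recording of "All SAEs that occur after any subject has been enrolled, before treatment, during treatment, or within 30 days following the cessation of treatment". Section 13.3 adds: "The safety reporting period ends at the time of the safety follow-up visit, 30 days after the last dose of study drug", or earlier if an investigational agent or anticancer therapy starts. Section 13.4 requires every SAE to be reported within 24 hours of awareness and the adverse event page of the case report form to be completed for a serious event. It states no end date.

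**The concern.** The primary objective of the escalation part of this first-in-human trial is safety and the maximum tolerated dose. The protocol singles out one late harm, hematologic second primary malignancy, and arranges blood counts for it after treatment ends. If a site finds such a case and reports it as serious, a reader would expect to see it in the study report. Under SAP 8.4.3 it would be in no adverse event listing once its onset is known to fall outside the window. The same holds for any other recorded SAE with known onset outside that window. The protocol's own all-SAE listing would have shown these events. The change is not identified as a departure from the protocol.

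**Working it through.** No sample size, power or error rate is involved. The check is a count of listings and a trace of cases through the written rules.

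**Count of listings**

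| Document | Listings | Limited to treatment-emergent events | Could hold an event with known onset after the window |
|---|---|---|---|
| Protocol 14.6.2 | all AEs; all SAEs; all AEs leading to discontinuation (3) | 0 of 3 | 2 of 3 (all AEs, all SAEs) |
| SAP 8.4.3 | all TEAEs; treatment-emergent SAEs; TEAEs leading to discontinuation (3) | 3 of 3 | 0 of 3 |

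The protocol's discontinuation listing is not counted in the last column, because an event that starts after treatment has ended cannot have caused treatment to stop.

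**Trace of one case.** Take, for illustration, a non-fatal second primary malignancy with known onset 60 days after the last dose, no new therapy, judged serious by the investigator.

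1. *Reporting.* The 30-day recording rule in 13.2.2 and the 13.3 reporting period have passed. Section 13.4 still applies: report within 24 hours of awareness and complete the case report form page. Protocol 8.3 also allows a subject who stops treatment to agree to continued collection of adverse events.
2. *All TEAEs.* Day 60 is beyond 30 days. The SAP counts from end of treatment, and the end-of-treatment visit may fall up to 7 days after the last dose. The latest arguable limit is therefore 30 + 7 = 37 days, and 60 is beyond that too. Not listed.
3. *Treatment-emergent SAEs.* Not treatment-emergent, so not listed.
4. *TEAEs leading to discontinuation.* Not listed, for the same reason.
5. *Default rule.* It applies only where treatment-emergence cannot be ascertained. Here the onset date is known.

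**Other SAEs that fall outside all three listings**

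- An SAE in a treated subject that began before the first dose and did not worsen afterwards. Section 13.2.2 requires it to be recorded.
- An SAE that starts after cytotoxic chemotherapy or another investigational agent but still within 30 days of stopping. Section 13.2.2 requires recording, while the SAP window has closed.
- The two late SAE types the protocol writes out itself: death suspected as delayed toxicity (13.2.2) and an SAE associated with pregnancy after study completion (13.5).

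**Cases that are not lost.** A malignancy with onset inside the window but discovered later is still recordable under 13.2.2 and still treatment-emergent. One whose treatment-emergence cannot be ascertained is listed by default.

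**Other SAP outputs.** The laboratory listings in 8.4.4 could show abnormal counts but not a diagnosis. Subsequent anticancer therapy (8.4.10) is marked not applicable. The disposition listing in 8.1 gives vital status, which would show a death but not the event behind it.

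**The case against.** **The window may be wider than assumed.** Its two limbs are joined by *or*, with no statement that the earlier one prevails. Read literally as alternatives, an event in a subject who has not started such therapy would be treatment-emergent however late it occurs, and those are largely the subjects whom 7.5.5 monitors. This is a fair reading of the words, and the count of 0 of 3 depends on rejecting it. It would make the 30-day limit pointless, and it conflicts with protocol 13.3, which takes the earliest of its end points. The truncating reading is the natural one. The ambiguity itself needs correcting.

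**The SAP speaks elsewhere of wider scope.** Section 8 says data for the first three dose levels will be listed, and 8.4.1 refers to all safety event data in phase 1a. These are general statements. The specific bullets in 8.4.3 define what will be produced.

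**The reduction is disclosed and the trial has ended.** SAP 2.2 announces a selection, the SAP governs, and the study was terminated by May 2024. This stands as a reason for low priority. It does not tell a reader that the all-SAE listing was dropped.

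**A stronger inference to avoid.** A reader might conclude that the protocol leaves a late second primary malignancy with no way of being recorded or reported. The documents do not support that. The duty in 13.4 has no end date, covers all SAEs and includes case report form entry, and the SAE definition in 13.2.2 includes important medical events. The 30-day windows sit awkwardly beside it, but the route exists. Section 7.5.5 merely lacks a cross-reference to it.

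**Conclusion.** The point holds as a minor one about the scope of the listings. The SAP replaces the protocol's all-AE and all-SAE listings with treatment-emergent ones without naming the change. On the natural reading of the window, a reported SAE with known onset outside it is in none of the three adverse event listings.

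This rests on two assumptions: that the missing unit is days, as in protocol 14.6.2, and that new therapy shortens the window. Onset at about days 31 to 37 after the last dose is arguable because of the end-of-treatment visit allowance; later onset is not.

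Nothing here shows that such a case occurred or is likely. The documents give no incidence and do not say how many subjects, if any, remain in follow-up. Dose-limiting toxicities are confined to cycle 1, so no such assessment or dose decision changes. What is at stake is whether the study report of a first-in-human trial would show a serious event that the sponsor already held.

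**What to change.** Two changes to SAP 8.4.3:

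1. List all recorded SAEs, whether or not treatment-emergent. Alternatively, keep the three listings and add one of SAEs and second primary malignancies with onset outside the TEAE window. Show dose level, days since last dose, and subsequent anticancer therapy where recorded. The therapy column matters because an event after new treatment is confounded.
2. Correct the window to run through 30 days after the end of treatment or until another investigational agent or cytotoxic chemotherapy starts, whichever occurs first.

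It would also help to state in SAP 2.2 that the protocol's all-AE and all-SAE listings are not reproduced in full, if that remains the intention.

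The cost is one extra or widened listing from data already recorded, which may turn out empty, plus a wording correction. No new visit or test is needed. A protocol amendment is not warranted: 13.4 already covers reporting and case report form entry, and amending a terminated study would need ethics and regulatory approval for the sake of a cross-reference. The general reduction of analyses after early termination can stay as it is.

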#### **8.4.4 Laboratory Values**

Laboratory assessments and specific clinical laboratory tests are described in detail in Section 13.1.8 of Protocol. Blood samples for the following clinical laboratory tests were collected:

- Hematology: Hemoglobin, hematocrit, WBC, differential blood count with ANC, platelet count, RBC.
- Serum chemistries: alkaline phosphatase, ALT, AST, total bilirubin, blood urea nitrogen, creatinine, bicarbonate, albumin, calcium, magnesium, glucose, phosphorus, total protein, and triglycerides.
- Coagulation: partial thromboplastin, partial thromboplastin time (PTT), aPTT, and international normalized ratio (INR).
- Urinalysis: glucose, blood, protein, and pH.

- Viral serology: HBV, HCV, HIV, and human T-cell lymphotropic virus 1 (HTLV-1).

The following listings for hematology, chemistry and coagulation, and urinalysis will be provided:

- Subject listings of all lab values
- Subject listings for Grade 3 and 4 lab values
- Subject listings for laboratory results  $< 0.25 \times \text{LLN}$  or  $> 2.5 \times \text{ULN}$

#### **8.4.5 Vital Signs**

Subject listing of heart rate, temperature, systolic blood pressure, and diastolic blood pressure will be provided:

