## 14.2. General Consideration for Statistical Analysis

This section is a summary of the planned statistical analyses of the most important endpoints including safety, PK, primary, and key secondary efficacy endpoints. A statistical analysis plan (SAP) will be finalized prior to final database lock. Should the SAP and the protocol be inconsistent with respect to any further planned analyses, the language of the SAP is governing.

In general, the data from Phase 1 dose escalation part and Phase 1b dose expansion part will be analyzed separately except the efficacy data from the subjects who receive the study drug at MTD in dose escalation part and are rolled over to the dose expansion part. Their efficacy data in Phase 1 part will be integrated in Phase 1b efficacy data analysis unless otherwise specified.

All tests of treatment effects will be conducted at a 2-sided alpha level of 0.05, unless otherwise stated. All tests of interactions will be conducted at a 2-sided alpha level of 0.1, and all confidence intervals (CIs) will be given at a 2-sided 95% level, unless otherwise stated.

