#### **14.6. Safety Analyses**

Safety of EJM0414 including DLT for the Phase 1 dose escalation part and all safety events data in both Phase 1 and Phase 1b dose expansion part.

DLT evaluation will be performed based on the DLT Population (Section 14.3) and the other safety analysis will be conducted on the Safety Population.

In general safety parameters will be summarized by the analysis group (see Section 14.4) according to the different phases of the trial. These parameters will consist of the incidence of deaths, adverse events, serious adverse events (SAE), adverse events leading to discontinuation, adverse events leading to dose modification, ECOG, ECGs, physical examination, vital signs, and specific laboratory abnormalities (worst grade).

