## 2.2. Changes to Analysis from Protocol

The study was terminated early based on a business decision. Only selected analysis detailed in the phase 1a portion of the protocol will be conducted.

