### 3. STUDY OBJECTIVES AND ENDPOINTS

Objectives	Endpoints
Part 1: Phase 1a Dose Escalation Phase	
Primary	

 
To evaluate the safety and MTD of IPN60210 when administered as monotherapy in participants with R/R MM or R/R DLBCL.
 
	
 
Adverse event assessment according to CTCAE 5.0, physical examination, vital signs (blood pressure, heart rate, respiration rate, and body temperature), 12-lead ECG, clinical laboratory tests (haematology including coagulation profile, serum chemistries, and urinalysis), ECOG performance status, concomitant medication monitoring, and DLTs.
 

Exploratory	

 
To investigate pharmacodynamic biomarkers of target engagement in tumour/bone marrow biopsy and/or blood.
 
	
 
Change from baseline of H3K36me3 in tumour/bone marrow biopsy and/or blood.
 

 
To explore potential predictive biomarkers of response and other biomarkers associated with mechanism of action or resistance in bone marrow aspirates, tumour/bone marrow biopsies, and/or blood samples.
 
	
 
Determination of biomarkers of response such as histones and histone methylation markers, genomic alterations such as somatic mutations, DNA methylation and other DNA alterations such as t(4;14), protein and gene expression, immune cells in bone marrow aspirates, tumour biopsies, and/or blood samples.
 

 
To assess PK of IPN60210 when administered as monotherapy in participants with R/R MM or R/R DLBCL.
 
	
 
PK parameters including but not limited to: <math>AUC_{0-t}</math>, <math>C_{max}</math>, <math>T_{max}</math>, and <math>\lambda_z</math>:
 

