### 7.2. Baseline Assessments

Unless otherwise specified, baseline is defined as the last non-missing (including unscheduled) assessment value prior to the initial administration of the study drug. If an assessment is performed on the same day as the first dose of study drug, and time is not collected, the assessment will be considered baseline. If there is more than one value on or prior to the initial administration of the study drug, the value closest to and prior to the receipt of the first dose, whether scheduled or unscheduled, will be used as the baseline value.

AEs and medications reported with a start date on the date of first dose will be considered to have occurred after the start of treatment. For vital signs (excluding weight and height) and ECG measures, baseline results will be identified for the set. Baseline will be determined separately for each laboratory analyte.

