#### **8.4.6 Electrocardiograms (ECGs)**

NA

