#### **8.4.8 Physical Examination**

NA

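### The SAP keeps ECG, respiration rate and ECOG in the Phase 1a primary safety endpoint, but plans no output for ECG intervals, respiration rate or post-baseline ECOG and does not record them as dropped

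*SAP*

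**What the plan says.** SAP Section 3 defines the Phase 1a primary safety endpoint. Besides adverse events, laboratory tests, concomitant medication and DLTs, it includes "physical examination, vital signs (blood pressure, heart rate, respiration rate, and body temperature), 12-lead ECG" and ECOG performance status.

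The output sections are narrower. SAP 8.4.5 reads: "Subject listing of heart rate, temperature, systolic blood pressure, and diastolic blood pressure will be provided". Respiration rate is not in it, and change from baseline is not mentioned. SAP 8.4.6 (ECG), 8.4.7 (ECOG) and 8.4.8 (physical examination) contain only NA. ECOG appears once more, in 8.2, as a baseline characteristic. SAP 7.2 still sets an ECG baseline: "For vital signs (excluding weight and height) and ECG measures, baseline results will be identified for the set". No output uses it, and nothing says how the three tracings of a triplicate are combined.

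On departures from the protocol, SAP 2.2 says that the study ended early for business reasons and adds: "Only selected analysis detailed in the phase 1a portion of the protocol will be conducted". It names no analysis that was dropped.

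Protocol 14.6 counted ECOG, ECGs, physical examination and vital signs among the safety parameters to be summarised by analysis group. Protocol 14.6.5 planned listings of ECOG, ECG and vital signs with change from baseline. For inconsistencies over planned analyses, protocol 14.2 provides that "the language of the SAP is governing".

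**The concern.** A programmer who follows the SAP exactly will produce no listing of ECG intervals (QTcF included), respiration rate or on-treatment ECOG, although all three stand in the primary safety endpoint of the same document. Because the SAP governs, the protocol's planned listings do not fill the gap. SAP Section 1 requires deviations from the SAP to be justified in the CSR. Leaving these values out is not a deviation from the SAP, so that safeguard would not prompt an explanation.

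This is a first-in-human study that stopped after three dose levels, so its individual safety values are most of what it can contribute. Protocol 5.3 relies on serial ECG, among other monitoring, for the risks it names, and protocol 7.5.2 ties follow-up to physical examination and respiration rate. Protocol 5.2.3.4 reports a QTc increase in dogs. Changes by dose level that are too small to be called adverse events are what a listing would show and an adverse event table would not.

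**Working it through.** **Step 1. Match each Section 3 component to a Section 8 output.**

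| Component in SAP 3 | Planned output | Omission marked? |
|---|---|---|
| Adverse events | 8.4.3, listings | not omitted |
| Laboratory tests | 8.4.4, listings | not omitted |
| Concomitant medication | 8.4.9, summary and listing | not omitted |
| DLTs | 8.4.1, on the DLT population | not omitted |
| Vital signs (4 named measures) | 8.4.5, 3 of 4; respiration rate absent | no |
| 12-lead ECG | 8.4.6, NA | yes, no reason given |
| ECOG | 8.4.7, NA; baseline only in 8.2 | yes, no reason given |
| Physical examination | 8.4.8, NA | yes, no reason given |

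Of 8 components, 4 are covered, 1 is covered in part and 3 are marked NA. The opening sentence of SAP Section 8, that data for the first three dose levels will be listed, names no component. The specific entries in 8.4.5 to 8.4.8 override it.

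**Step 2. What still reaches an output through adverse events.** Protocol 7.5.3 requires interruption when QTcF above 500 msec, or prolongation of more than 60 msec from baseline, is observed and confirmed. Protocol 13.2.7.2 says that a safety assessment leading to interruption should be recorded as an adverse event, and 13.2.4 requires the same for clinically significant assessments. SAP 8.4.3 lists all TEAEs. Confirmed crossings should therefore appear as event terms. The measured intervals, unconfirmed readings and smaller changes do not. New clinically significant examination findings must also be recorded as adverse events (protocol 13.1.6).

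**Step 3. Scheduled values without an output**, as a maximum for one escalation subject who completes Cycles 1 and 2.

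- *ECG.* Table 8 footnote e refers Cycle 1 and 2 ECGs to Table 9. Time points there: pre-dose 7 + 30 min 2 + 1 h 2 + 2 h 7 + 4 h 2 + 6 h 2 + 24 h 2 = 24. Less the Cycle 1 Day 1 pre-dose set (baseline): 24 − 1 = 23. In tracings: 23 × 3 = 69.
- *Respiration rate.* Serial sets in Table 9: 6 on Cycle 1 Day 1 + 6 on Cycle 2 Day 1 = 12, less the Cycle 1 Day 1 pre-dose set = 11. Single sets in Table 8: Cycle 1 Days 2, 3, 4, 8, 15, 22 = 6; Cycle 2 Days 2, 8, 15 = 3. Total 11 + 6 + 3 = 20, with the Day 1 entries of Table 8 counted inside the serial sets.
- *ECOG.* Table 8: Cycle 2 Day 1 = 1.
- *End of treatment and safety follow-up* (Table 8) add up to 1 triplicate ECG, 2 respiration-rate readings and 2 ECOG assessments.

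**Step 4. Nonclinical context for the dose levels studied.** Protocol 5.2.3.4 puts the start of the dog cardiovascular effects at about 1.2 to 2.5 times the predicted human efficacious unbound Cmax for a 120 mg dose. If exposure is proportional to dose (an assumption), the three levels correspond to 100/120 = 0.83, 200/120 = 1.67 and 300/120 = 2.5 times that reference. So 200 mg lies within the band and 300 mg at its upper edge. The 200 mg level stays at or above 1.2-fold down to 1.2/1.667 = 72% of proportional exposure, and 300 mg down to 1.2/2.5 = 48%.

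**The case against.** The best defence is that this is a deliberately reduced plan for a terminated study and that it says so. Section 2.2 announces a selection, and the NA entries under their own headings show a reader that ECG, ECOG and examination outputs were switched off. Section 3 also carries forward biomarker objectives that 9.2 says will not be analysed, so it may be read as a restatement of protocol objectives rather than a promise of output. Most of this stands. A reduced set is permitted, and three of the four omissions are visible. It does not explain respiration rate, which disappears with no marker. Nor does it supply a reason for any item in the section headed as changes from the protocol.

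A reader might infer more than the documents support:

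- *That serious QTcF events would go unreported.* By Step 2, confirmed crossings should already be in the TEAE listings.
- *That these values can reach the CSR only as adverse events.* The documents fix the planned statistical output, not everything in the CSR. Protocol 14.6.1 itself describes DLT and MTD evaluation in the CSR outside any statistical output.
- *That monitoring of subjects was weakened.* Protocol 5.3 and 7.5.2 concern care during treatment, and an SAP dated after termination does not alter that.
- *That the animal data point to harm at these doses.* The protocol judged the dog QTc increase not clinically significant, and the follow-up 28-day dog study showed no ECG effects. Respiration rate fell in rats only at the high dose, 7- to 15-fold the predicted efficacious level. The main consistent dog findings, lower arterial and pulse pressure with higher heart rate, are in measures that 8.4.5 does list.
- *That physical examination is an equal gap.* Protocol 14.6.5 planned no listing of it, and new clinically significant findings must be recorded as adverse events.

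**Conclusion.** The point holds as a mismatch within the SAP over its primary safety endpoint. ECG intervals, respiration rate and post-baseline ECOG remain in Section 3, have no planned statistical output, and are not named as dropped in 2.2. The loss is of measured values and of unconfirmed or sub-threshold changes, not of clinically significant events. Its size is bounded by the schedule: up to 23 triplicate-ECG time points, 20 respiration-rate readings and 1 ECOG assessment per subject through Cycle 2, plus the end-of-treatment and follow-up visits. The documents give neither the number of subjects treated nor the number of assessments obtained, so the actual total cannot be stated. The conclusion on events assumes that investigators recorded adverse events as protocol 13.2.4 and 13.2.7.2 require. The case is strongest for ECG and respiration rate. It should be corrected before the CSR is written.

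**What to change.** - **8.4.5:** add respiration rate to the vital-signs listing.
- **8.4.6:** replace NA with a listing of ECG intervals, QTcF included, by dose level, with change from the 7.2 baseline. State how triplicates are combined for that change, for example as the mean of the three tracings at baseline and at each time point.
- **8.4.7:** replace NA with a listing of post-baseline ECOG.
- **2.2 and 3:** for any of these items that the sponsor still omits, name it in 2.2 with the reason and align Section 3. The same applies to change from baseline in vital signs, which protocol 14.6.5 planned.
- **Physical examination:** a statement in 2.2 that findings are reported through adverse events is enough.

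The cost is one column, up to two listings and a sentence on triplicates, from assessments the protocol already scheduled. This assumes that the data were collected and entered, which the documents do not state. If they were not, naming the omissions costs a few sentences.
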